9.3.2 Follow-up of pregnancy

Any pregnancies must be followed-up to their conclusion and the outcome must be reported to the sponsor's Global Drug Safety department.

Any AE associated with the pregnancy occurring during the follow-up period after study treatment administration must be reported on separate AE pages in the CRF. Any SAE occurring during the pregnancy must be reported on an SAE form as described in Section 9.3.1.

9.4 Study safety monitoring

Study safety information (AEs, SAEs, laboratory values, ECGs, vital signs, and study-specific examinations as required) is monitored and reviewed on a continuous basis by the sponsor's clinical team (in charge of ensuring subjects' safety as well as data quality). In addition, a Safety Event Committee is monitoring safety data [see Section 3.4].

10 STATISTICAL METHODS

All statistical analyses will be conducted by the sponsor or by designated CROs supervised by the sponsor.

A statistical analysis plan (SAP) will provide full details of the analyses, data displays, and algorithms to be used for data derivations.

Any deviation(s) from the original statistical plan described hereafter will be described and justified in the SAP or in the CSR, as appropriate.

10.1 Analysis sets

10.1.1 Screened analysis set

The Screened analysis set includes all subjects who are screened and have a subject identification number.

10.1.2 Randomized analysis set

The Randomized analysis set includes all subjects who have been assigned to a double-blind study treatment.

10.1.3 Full analysis set

The Full analysis set (FAS) includes all randomized subjects who have been administered the study treatment.

In order to adhere to the intention-to-treat principle as much as possible:

- Subjects are evaluated according to the study treatment they have been assigned to (which may be different from the study treatment they have received),
- All available data are included.

10.1.4 Per-protocol analysis set

The Per-protocol set (PPS) comprises all subjects from the FAS who complied with the protocol sufficiently to allow adequate estimation of the treatment effects. Criteria for sufficient compliance include exposure to treatment, availability of key endpoints measurements and absence of major protocol deviations that have an impact on the treatment effect.

The full list of criteria will be detailed in the SAP before making the full randomization information available.

10.1.5 Safety set

The Safety set (SS) includes all subjects who received study treatment. Subjects will be evaluated according to the actual treatment they received, which may differ from the randomly assigned treatment.

10.1.6 Pharmacokinetic analysis set

The PK analysis set includes all subjects in the SS who have at least one PK sample collected after administration of study treatment.

10.1.7 Usage of the analysis sets

The PD analysis will be performed on the FAS based on the study treatment as randomized. Sensitivity analyses will be conducted using same endpoints as specified in Section 10.3 on the PPS.

Safety analyses will be performed on the SS based on actual study treatment received.

Subject listings will be based on the SS, unless otherwise specified. Subject disposition will be described for the Screened analysis set.

[Table 4](#) describes the analysis sets used for the analysis of each data set.

Table 4 Analysis datasets

Analysis	Screened set	RND	FAS	PPS	SS	PK set
Subject disposition	X					
Baseline and disease characteristics		(x)	X	(x)		
Previous and concomitant medication			X			
Study treatment exposure			X	(x)		
PD endpoints analyses			X	(x)		
Safety and tolerability analyses						X
PK data analysis						X

Note: Selected safety parameters, X: main analysis, (x): Sensitivity analysis to be conducted only if > 10% difference of set size with set used for main analysis.

FAS, Full analysis set; PD, Pharmacodynamic; PK, Pharmacokinetic; PPS, Per-protocol set; RND, Randomized set; SS, Safety set.

10.2 Variables

The *absolute change from baseline to time T* is defined as the algebraic difference between the value observed at time T minus the value at baseline.

The *relative change from baseline to time T* is defined as the ratio of the absolute change from baseline to time T on the baseline value.

Unless specified otherwise, the *baseline value* is defined as the arithmetic mean of the last 2 values collected during the screening phase prior to randomization.

10.2.1 Primary efficacy variable(s)

Not applicable.

10.2.2 Key secondary efficacy variables

Not applicable.

10.2.3 Safety variables

10.2.3.1 Adverse events

An AE is defined as any event that is recorded on the AE CRF module regardless of the onset date.

TEAEs are those AEs with onset date/time \geq date/time of first study treatment administration and \leq 48 h after date/time of last study treatment administration.

The handling of missing or incomplete date/time of AEs and assessments will be described in the SAP.

10.2.3.2 Laboratory data

Laboratory analyses are based on data received from the central laboratory [see Section 7.2.5.2]. All transferred central laboratory data are taken into account regardless of whether they correspond to scheduled or unscheduled assessments.

Baseline laboratory test refers to the latest laboratory test performed prior to the first study treatment administration.

End-of-treatment laboratory test refers to the laboratory test performed on the day following the day of study treatment administration (Visit 3).

For each continuous laboratory parameter, the following variables will be summarized:

- Absolute value at each time point,
- Absolute change from baseline to each time point,
- Treatment-emergent marked laboratory abnormalities (i.e., up to 48 h after study treatment administration).

For categorical laboratory parameters, the following variables will be summarized:

- Proportion of subjects by categories at each time point.

Unless stated otherwise, no imputation for missing laboratory values will be performed.

10.2.3.3 ECG

ECG recording is performed at the time points described in [Table 3](#).

- Treatment-emergent ECG abnormalities (i.e., up to 48 h after study treatment administration).
- Absolute change from baseline to each time point in ECG variables: HR, and the intervals: PQ/PR, QRS, QT, RR, QTcB, and QTcF.

10.2.3.4 Vital signs

- Absolute value in vital signs at each assessed time point during the study.
- Relative change from baseline to each measured time point in vital signs (systolic and diastolic arterial BP and pulse rate).

10.2.4 Pharmacokinetic and pharmacodynamic variables

10.2.4.1 Pharmacokinetic variables

Plasma concentrations per time point will be listed by treatment arm and subject, and summarized by time point and dose group using arithmetic and geometric mean,

minimum, median, maximum, standard deviation (SD), standard error (SE), and 2-sided 95% confidence interval (CI) of the means and coefficient of variation (CV) in %.

PK parameters will be derived using non-compartmental methods:

- C_{max} , t_{max} , and AUC_{0-24h} will be listed by dose group and subject and will be summarized by dose group.
- C_{max} , t_{max}^* , and AUC_{0-24h} will be summarized with arithmetic mean, geometric mean, minimum, median, maximum, SD, SE, CV (%), and 95% CI of the arithmetic and geometric means.
(* For t_{max} the geometric mean and its 95% CI will not be calculated).
- Log-transformed C_{max} and AUC_{0-24h} values will be summarized with mean and SD of the logs.

10.2.4.2 Pharmacodynamic variables

The primary PD variable is the IPA as measured by VerifyNow® at each time point, as described in table of assessments [Table 2 and Table 3].

The primary PD endpoint is the *PD response* that is defined for each subject as a $PRU < 100$ starting 30 min after injection and lasting for at least 3 h, as measured via VerifyNow®.

Additional PD variables related to the main ones will also be considered at each time point:

- Extent of aggregation (measured through LTA).
- Absolute PRU values (for VerifyNow®).
- % of subjects at 8 h after study treatment injection with PRU value < 100 or $> 1.05 \times$ baseline value.

10.3 Description of statistical analyses

All analyses will be conducted by treatment arm on the FAS, i.e., ACT-246475 8 mg, ACT-246475 16 mg, and placebo.

10.3.1 Overall testing strategy

The study is intended to assess the effect of ACT-246475 on platelet aggregation.

The primary null hypotheses will be tested at a 0.025 alpha level for each comparison to placebo, and then, if the null hypothesis is rejected for at least 1 of the 2 active arms, it will be completed by testing in each active arm that the proportion of patients achieving a response is statistically greater than 70%.

The study will be declared to be positive with regard to the primary objective if, for at least 1 of the 2 active arms, the 2 null hypotheses are sequentially rejected at an adjusted alpha level of 0.025.

No imputation will be considered for handling missing values in the main analysis of PD. Imputations may be performed in sensitivity/exploratory analyses, if deemed necessary, e.g., if more than 10% missing values at a given time point.

10.3.2 Analysis of the primary pharmacodynamic variable

The study is designed to demonstrate that ACT-246475 treatment enables a large proportion (a target of 85%) of the enrolled subjects to achieve a clinically meaningful level of IPA, i.e., PRU < 100.

10.3.2.1 Hypotheses and statistical model

The primary goal is to determine that the proportion p of subjects receiving a dose of ACT-246475, who achieve the PD response as measured by VerifyNow®, is statistically greater than 70%.

In order to achieve this objective, the testing strategy will consider a sequential approach demonstrate a statistically significant difference between the control arm (placebo) and at least 1 of the active arms, then to confirm that the observed response rate (P_r) in the same active arm is statistically significantly greater than the predefined response rate.

The comparison of each of the 2 active treatment arms will be conducted vs placebo, with the following hypotheses:

$$H_{p0HD}: p_{placebo} = p_{HD}$$

vs

$$H_{p1HD}: p_{placebo} \neq p_{HD}$$

AND

$$H_{p0LD}: p_{placebo} = p_{LD}$$

vs

$$H_{p1LD}: p_{placebo} \neq p_{LD}$$

Where, $p_{placebo}$ is the proportion of responders in Placebo arm, p_{HD} is the proportion of responders in the ACT-246475 16 mg arm, and p_{LD} is the proportion of responders in the ACT-246475 8 mg arm.

The 2 null hypotheses will be tested for each dose by a 2-sided z-test at an overall significance level (alpha) of 0.05 adjusted for multiplicity using the Bonferroni method, i.e., 0.025 for each comparison.

Assuming that either H_{p0HD} , or H_{p0LD} , or both are rejected, then the following hypotheses will be tested for each of the active doses that were statistically significantly different from placebo:

$$H_0: P_{\text{responders}} = 0.70$$

vs

$$H_1: P_{\text{responders}} > 0.70$$

The null hypothesis will be tested for each dose by a 1-sided z-test at an overall significance level (alpha) of 0.05 adjusted for multiplicity using the Bonferroni method, i.e., 0.025 for each comparison.

10.3.2.2 Handling of missing data

Subjects for whom determination of the response is not possible will be counted as non-responders in the main analysis; no other imputation will be considered.

10.3.2.3 Main analysis

The primary statistical analysis will be performed on the FAS population for each dose level.

The first set of null hypotheses (H_{p0HD} and H_{p0LD}) will be tested for each dose by a 2-sided z-test at an overall significance level (alpha) of 0.05 adjusted for multiplicity using the Bonferroni method, i.e., 0.025 for each comparison.

The second null hypothesis (H_0) will be tested for each dose by a 1-sided z-test. The estimated proportion of responders in each arm and the corresponding 95% CI will be provided.

A longitudinal analysis of the treatment effect, from start of treatment up to 8 h after injection, on platelet reactivity as measured by VerifyNow®, i.e., PRU value, will be performed using a mixed model with PRU as the dependent variable, subject as a random factor, and treatment (8 mg, 16 mg, and placebo), injection site (abdomen, thigh), PRU level at randomization (stratification levels), age (continuous), gender (male, female), and assessment time (continuous) as fixed factors. The model will also include (treatment \times injection site) as an interaction term to assess consistency of treatment effect across injection sites.

A logistic regression analysis of the PD response will be performed using the same factor as covariates.

Summary of PD response, in terms of number (%) of subjects, will be provided. IPA as measured by VerifyNow® will also be summarized as a continuous parameter.

10.3.2.4 Supportive/sensitivity analyses

The consistency across the following subgroups will be assessed by repeating the primary endpoint analysis, assuming there are a sufficient number of subjects:

1. Age: < 55 vs ≥ 55 years
2. Body mass index: < 25.0 vs (≥ 25.0 and < 30.0) vs ≥ 30.0 kg/m²
3. Sex: male vs female
4. Diabetes mellitus at baseline: yes vs no
5. Chronic kidney disease: yes vs no

An additional analysis of the supportive PD endpoint (LTA-PD response) will be conducted using the same approach as described for the primary PD analysis.

Further analyses will be described in the SAP as necessary.

10.3.3 Analysis of key secondary efficacy variable(s)

Not applicable.

10.3.4 Analysis of the safety variables

Unless noted otherwise, the SS will be used for summaries and listings of safety data.

10.3.4.1 Adverse events

AEs coded using the most recent version of MedDRA, will be summarized (frequency counts and percentages) by system organ class and/or preferred term, and maximum intensity.

Summaries will be provided for the following data:

- TEAEs.
- TEAEs related to study treatment.
- Treatment-emergent non-serious AEs.
- Treatment-emergent SAEs.
- Treatment-emergent SAEs related to study treatment.
- TEAEs with fatal outcome.
- TEAEs related to study treatment with fatal outcome.

10.3.4.2 Laboratory data

Unless noted otherwise, summaries and listings will include unscheduled assessments reported by the central laboratory.

Descriptive summary statistics by scheduled visit will be provided for observed values and absolute changes from baseline in both hematology and blood chemistry laboratory variables.

The absolute change from baseline to each time point for hematology and blood chemistry variables will be summarized.

Number (%) of subjects with treatment-emergent marked laboratory abnormalities will be tabulated and all marked laboratory abnormalities will be listed.

10.3.4.3 Vital signs, weight and physical examination

Each summary and listing will include unscheduled assessments.

Absolute changes from baseline to last value on study treatment in vital signs will be summarized. The absolute values at each time point will also be summarized.

Physical examination abnormalities will be listed.

10.3.4.4 Electrocardiograms

Each ECG summary and listing will include unscheduled assessments.

The absolute change from baseline to each time point for ECG variables will be summarized. The absolute values at each time point will be summarized.

Number (%) of subjects having a marked ECG abnormality during the treatment period will be summarized.

All ECG values for subjects with at least one marked ECG abnormality will be listed.

10.4 Interim analyses

No interim analysis planned.

10.5 Sample size

The sample size is based on the primary PD endpoint, which is the proportion of subjects achieving a predefined PD response as measured by VerifyNow®. The computation of the sample size was performed using the East 6.0 software (version 6.4.0.1, 30 Aug. 2016) from Cytel.

This study includes 3 treatment arms, 2 active arms (ACT-246475 8 mg and 16 mg) and a placebo arm comprising the 2 dose-matching placebo groups.

The primary objective is to assess the effectiveness of ACT-246475 to allow subjects to achieve a predefined PD response, therefore the sample size will be provided in order to reach the necessary power to sequentially demonstrate that at least 1 of the 2 doses has a higher response rate than placebo and that this response rate is statistically significantly greater than the proportion of responders under H_0 .

The sample size required for demonstrating a difference to placebo is based on an overall alpha of 0.05 (2-sided), adjusted for multiplicity using a Bonferroni method to 0.025 for each comparison, and a power of 0.9; the assumptions related to response rate under the null and alternative hypotheses are reported in the table below:

Proportion of responders under H_0 (placebo)	Proportion of responders under H_1 (active)	Number of subjects (total)	Number of subjects (per arm)
50%	75% (odds ratio of 3)	288	96

The sample size required to demonstrate that the achieved response rate is different from 70% is based on a 2-sided type I error (alpha) of 0.025, and a power of 0.9; the assumptions related to response rate under the null and alternative hypotheses, are reported in the table below:

Proportion of responders under H_0	Proportion of responders under H_1	Number of subjects (total for the 2 active arms)	Number of subjects (per arm)
70%	85%	196	98

Therefore the study should include at least 98 subjects evaluable for the primary PD endpoint in each treatment arm. Assuming a rate of drop-out or non-evaluable data of about 10%, each arm will include 108 subjects leading to a total for the study of 324 subjects.

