	
Summary of PD response, in terms of number (%) of subjects, will be provided. IPA as measured by VerifyNow® will also be summarized as a continuous variable.
 
Supportive/sensitivity analyses
 
Consistency across the following subgroups will be assessed by repeating the primary endpoint analysis, assuming relevant number of subjects:
 
• Age: < 55 vs \geq 55 years• Body mass index: < 25.0 vs (\geq 25.0 and < 30.0) vs \geq 30.0 kg/m^2• Sex: male vs female• Diabetes mellitus at baseline: yes vs no• Chronic kidney disease: yes vs no 
Additional analyses of the supportive PD endpoint (light transmission aggregometry-based PD response) will be conducted using the same approach as described for the primary PD analysis.
 
Sample size
 
The primary objective is to assess the effectiveness of ACT-246475 to allow subjects to achieve a predefined PD response; therefore, the sample size provided is sufficient to sequentially demonstrate that at least 1 of the 2 ACT-246475 doses has a higher response rate than placebo and that this response rate is greater than 70%.
 
The sample size required for demonstrating a difference to placebo, based on an overall type I error of 0.05 (2-sided), adjusted for multiplicity using a Bonferroni method to 0.025 for each comparison, a power of 90%, a response rate of 50% under H_0 (placebo) and 75% under H_1 is 96 per arm.
 
The sample size required to demonstrate that the response rate is different from 70% is based on a 2-sided type I error of 0.025, a power of 90%; and the assumptions of a response rate of 70% under H_0 and 85% under H_1 is 98 per arm.
 
The study should include at least 98 subjects in each treatment arm, and assuming a rate of drop-out or non-evaluable data of

--	---

	about 10%, 108 subjects should be included in each arm, giving a total of 324 subjects enrolled in the study.

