6.8.1.2 Analysis

The analyses described in this section consider the primary endpoint, i.e., PD response. Sensitivity analysis of the other estimands are described in the sensitivity analyses section.

Unless stated otherwise, all analyses will be conducted on the FAS.

The study is designed to demonstrate that at least one dose of ACT-246475 enables a large proportion (a target of 85%) of the randomized subjects to achieve a clinically meaningful level of IPA, defined as a PRU < 100.

Hypotheses and statistical model

The primary goal is to determine that the proportion (p) of subjects receiving a dose of ACT-246475, who achieve the PD response as measured by VerifyNow®, is statistically greater than 70%.

To achieve this objective, the testing strategy considers a sequential approach to demonstrate a statistically significant difference between the control arm (placebo) and at least 1 of the active arms, then to confirm that the observed response rate (P_r) in the same active arm is significantly statistically greater than the predefined response rate.

The comparison of each of the 2 active treatment arms will be conducted vs placebo, with the following hypotheses:

$$H_{p0_{HD}}: p_{placebo} = p_{HD} \quad \text{vs} \quad H_{p1_{HD}}: p_{placebo} \neq p_{HD}$$

$$H_{p0_{LD}}: p_{placebo} = p_{LD} \quad \text{vs} \quad H_{p1_{LD}}: p_{placebo} \neq p_{LD}$$

Where, $p_{placebo}$ is the proportion of responders in placebo arm, p_{HD} is the proportion of responders in the ACT-246475 16 mg arm and p_{LD} is the proportion of responders in the ACT-246475 8 mg arm.

Assuming either $H_{p0_{HD}}$, or $H_{p0_{LD}}$, or both are rejected, then the following hypotheses will be tested for each of the active doses that was statistically significantly different from placebo:

$$H_0: P_{responders} = 0.70 \quad \text{vs} \quad H_1: P_{responders} = 0.85.$$

Main analysis

The first set of null hypotheses ($H_{p0_{HD}}$ and $H_{p0_{LD}}$) will be tested each using a 2-sided z-test at an overall significance level (alpha) of 0.025, corresponding to an overall alpha level of 0.05 adjusted for multiplicity using the Bonferroni method.

Each of the second null hypotheses ($H_{0_{HD}}$ and $H_{0_{LD}}$) will be tested by a 1-sided z-test at an overall significance level (alpha) of 0.05 adjusted for multiplicity using the Bonferroni method, i.e., 0.025 for each comparison.

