6.8.3 Handling of missing data

Subjects for whom determination of the PD response is not possible will not be included in the computation of response rate for the main analysis, however they will be counted as non-responders in the sensitivity analysis.

No other imputations are planned.

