11.3 Clarifications concerning endpoint definitions and related variables or statistical methods

Not applicable.

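### The sample-size text sizes the test against 70% at 2-sided 0.025 for 90% power, but the planned test is 1-sided 0.025 per dose and has about 95% power at 98 per arm (minor, conservative)

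*Protocol*

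**What the plan says.** The study is declared positive if, for at least one dose, two tests succeed in order: a comparison with placebo, then a test that the response rate in that arm exceeds 70%. This point concerns the second test.

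- **Sizing.** Protocol 10.5 states that the calculation "is based on a 2-sided type I error (alpha) of 0.025, and a power of 0.9", with response rates of 70% and 85%, and arrives at 98 per arm (196 for the two active arms). The synopsis, reproduced in SAP Appendix A, says that it "is based on a 2-sided type I error of 0.025, a power of 90"% and gives the same 98. With about 10% drop-out or non-evaluable data, 98 becomes 108 enrolled per arm.
- **Test, protocol.** Section 10.3.2.1 sets the alternative as a rate above 0.70 and says: "The null hypothesis will be tested for each dose by a 1-sided z-test at an overall significance level (alpha) of 0.05", split to 0.025 per dose by Bonferroni. Section 10.3.2.3 repeats that the test is 1-sided.
- **Test, SAP.** Section 6.8.1.2 says that each of these hypotheses "will be tested by a 1-sided z-test at an overall significance level (alpha) of 0.05 adjusted for multiplicity using the Bonferroni method", again 0.025 per dose. It writes the alternative as a rate equal to 0.85.
- **Synopsis analysis text.** It gives 0.025 for this test without stating sidedness.
- **Disclosure.** The SAP section headed "Clarifications concerning endpoint definitions and related variables or statistical methods" is marked not applicable, and nothing else in SAP section 11 mentions the difference.

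**The concern.** A 2-sided test at 0.025 puts 0.0125 in the upper tail. A 1-sided test at 0.025 puts all 0.025 there. These are different rejection rules for the hypothesis that decides whether the study is positive, and the documents attach the sample size to one and the analysis to the other.

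Two things are at stake. The design power quoted for the deciding step is not that of the test to be run. And a reader who takes the sizing text as the design would apply a stricter pass mark than the analysis sections do, so a result falling between the two marks could be disputed afterwards.

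**Working it through.** **Inputs.** p0 = 0.70, p1 = 0.85, power 0.90, n = 98 evaluable and 108 enrolled per arm (Protocol 10.5). Upper-tail alpha is 0.0125 as sized (Protocol 10.5) and 0.025 as planned (Protocol 10.3.2.1, SAP 6.8.1.2). Null variance 0.70 × 0.30 = 0.21; alternative variance 0.85 × 0.15 = 0.1275. Assumption: the z-test uses the null variance. The documents say only that it is a z-test.

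**Formulas.**

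n = (z_a·√0.21 + z_0.90·√0.1275)² / 0.15²

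Power = P(Z > (z_a·√(0.21/n) − 0.15) / √(0.1275/n))

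**Step 1: reproduce the plan's figure.** With upper tail 0.0125, z_a = 2.2414 and z_0.90 = 1.2816. This gives n = 97.98, so 98. Power at 98 is P(Z > −1.282) = 0.900. The stated 98 and 90% are reproduced exactly for the alpha written beside them.

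**Step 2: the planned test.** With upper tail 0.025, z_a = 1.9600. This gives n = 81.69, so 82. Power at 98 is P(Z > −1.643) = 0.950.

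**Step 3: both tests side by side.** Exact figures are binomial, at a true rate of 0.85.

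| Upper-tail alpha | n per arm | Power, normal approx. | Pass mark | Exact power | Exact size at 0.70 |
|---|---|---|---|---|---|
| 0.025 (planned) | 82 | 0.901 | 66/82 | 0.900 | 0.0223 |
| 0.025 (planned) | 98 | 0.950 | 78/98 | 0.945 | 0.0220 |
| 0.025 (planned) | 108 | 0.968 | 85/108 | 0.971 | 0.0280 |
| 0.0125 (as sized) | 98 | 0.900 | 79/98 | 0.909 | 0.0122 |
| 0.0125 (as sized) | 108 | 0.932 | 87/108 | 0.919 | 0.0090 |

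With the observed variance instead of the null variance, the planned pass mark would be 77/98 and would stay at 85/108.

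**Step 4: what the 95% depends on.** It needs a true rate of 85% in the analysis denominator. Protocol 10.3.2.2 says that subjects whose response cannot be determined "will be counted as non-responders in the main analysis; no other imputation will be considered". SAP 6.8.3 says that they "will not be included in the computation of response rate for the main analysis". The response algorithm in SAP 6.8.1.1 codes every subject who does not meet its conditions as a non-responder, which sides with the protocol.

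Suppose the non-responder rule applies, 98 of 108 are evaluable, and 85% of those 98 respond. Of the 10 lost, only dosed subjects stay in the full analysis set (FAS), which is limited to subjects given study treatment. The expected rate is 0.85 × 98 / (FAS n):

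| Of 10 lost, undosed | FAS n | Expected rate | Power, 1-sided 0.025 |
|---|---|---|---|
| 0 | 108 | 0.771 | 0.354 (exact 0.399) |
| 5 | 103 | 0.809 | 0.70 |
| 8 | 100 | 0.833 | 0.88 |
| 10 | 98 | 0.850 | 0.950 |

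**The case against.** The strongest reply is that no arithmetic is wrong. For the alpha it names, the sample-size text is correct, and only the sidedness differs from the analysis sections. The discrepancy is also conservative, and the study is described as exploratory Phase 2. A power sentence that understates power cannot bias the test. All of that stands, and it is why the point is minor. It does not remove the point: the alpha and power reported for the deciding step are still those of a test that will not be run.

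The source of 98 cannot be proved without the software output. A formula using the null variance throughout, at 1-sided 0.025, gives 98.07, which rounds up to 99, so a mislabelled sidedness cannot be fully excluded. In that case too, the sizing text would disagree with the test.

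A reader might infer two stronger things. The first is that the trial is underpowered on this step. The sidedness mismatch points the other way: 98 exceeds the 82 that the planned test needs. The second is that the missing-data rule cuts power to 35–40%. That is only the worst case, with all 10 lost subjects dosed. Protocol 10.5 allows for drop-out as well as non-evaluable data, undosed subjects leave the FAS, and the documents do not give the split. Nor do they settle whether non-evaluable subjects are excluded, so a corrected power sentence should not presume it.

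**Conclusion.** The inconsistency is real and minor. Both full definitions of the test agree on 1-sided 0.025 per dose, so the rejection rule is clear and the sizing text is what does not match it. At a true rate of 85% and with the null variance assumed, power is about 95% per dose at 98 in the denominator, against the stated 90%; 82 per arm would give 90%. The sample size and the planned pass mark (78/98 or 85/108) stand.

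The 95% is conditional on the unresolved handling of non-evaluable subjects. Under the non-responder rule with 98 of 108 evaluable, power lies anywhere from about 35% to about 95%, depending on how many of the 10 lost subjects were dosed. That conflict is a separate issue and does not arise from the sidedness mismatch.

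**What to change.** Keep the 1-sided test at 0.025 per dose. Restate the sizing as: 1-sided 0.025 per dose, power about 95% at a true response rate of 85% among 98 subjects in the analysis denominator. Name the variance used in the z-test. In the same place, write the SAP alternative as a rate above 0.70, as the protocol does, instead of equal to 0.85.

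This can be a wording amendment or one entry in SAP section 11. Protocol section 10 provides the second route: "Any deviation(s) from the original statistical plan described hereafter will be described and justified in the SAP or in the CSR". The cost is that one entry; the sample size, the data collected and the pass mark are untouched.

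If the sponsor in fact intended the sizing alpha, Protocol 10.3.2.1 and SAP 6.8.1.2 must instead be changed to 1-sided 0.0125 before unblinding. That option is not neutral: it raises the pass mark to 79/98 or 87/108.

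Reconcile Protocol 10.3.2.2 and SAP 6.8.1.1 with SAP 6.8.3 separately, and cross-refer from the power sentence to whichever rule is adopted.

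### The 90% power stated for the 70% responder test depends on a missing-response rule on which the protocol and SAP disagree

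*Protocol*

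**What the plan says.** **Sizing.** Protocol 10.5 bases the sample size on two tests per dose. For the comparison with placebo, the synopsis gives "a response rate of 50% under H_0 (placebo) and 75% under H_1 is 96 per arm", and 10.5 describes the alpha as "adjusted for multiplicity using a Bonferroni method to 0.025 for each comparison, and a power of 0.9". For the test against 70%, the synopsis gives "response rate of 70% under H_0 and 85% under H_1 is 98 per arm", and according to 10.5 this calculation "is based on a 2-sided type I error (alpha) of 0.025, and a power of 0.9". The larger number governs: "Therefore the study should include at least 98 subjects evaluable for the primary PD endpoint in each treatment arm". The allowance follows: "Assuming a rate of drop-out or non-evaluable data of about 10%, each arm will include 108 subjects", 324 in all.

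**Missing response.** Four places bear on the main analysis:
- Protocol 10.3.2.2: "Subjects for whom determination of the response is not possible will be counted as non-responders in the main analysis". The analysis set is the FAS, meaning all randomized and dosed subjects (protocol 10.1.3).
- Protocol 10.3.1: no imputation of missing values in the main PD analysis.
- SAP 6.8.3: subjects whose response cannot be determined "will not be included in the computation of response rate for the main analysis". They become non-responders only in the sensitivity analysis.
- SAP 6.8.1.1: the algorithm tolerates one missing intermediate value (1 h or 2 h). A subject missing both falls to the final branch and is coded NO.

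**Declared changes.** Protocol section 10 allows departures from its statistical plan if they are described and justified in the SAP or the study report. SAP 11.1 lists one change, to the 8-hour variable. SAP 11.3 and 11.4 are marked not applicable.

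**The 85%.** Protocol 10.3.2 states the 85% target as a share of enrolled subjects, and SAP 6.8.1.2 as a share of randomized subjects. Protocol 10.5 ties the 98 to evaluable subjects.

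**The concern.** Adding about 10% to an evaluable sample size protects power only if the lost subjects leave the denominator. If they stay in as failures, the response rate itself falls. The margin over 70% is 15 points at 85%, and each percentage point of imputed failure removes 0.85 of a point. Adding subjects in proportion to the loss does not offset that.

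The test against 70% is what protocol 10.3.2.1 calls the primary goal, and the study is positive only if at least one dose passes both tests. The unresolved rule therefore affects both the power claim and the denominator of the primary result. Near the 70% boundary, the choice between excluding and failing such subjects could change the conclusion.

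**Working it through.** **Inputs.** p0 = 0.70, p1 = 0.85, sizing alpha 0.025 two-sided (upper tail 0.0125, z = 2.2414), power 0.90 (z = 1.2816), about 10% loss, 108 per arm: all from protocol 10.5. Test as planned: one-sided 0.025 per dose (z = 1.9600), from protocol 10.3.2.1 and SAP 6.8.1.2.

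**Reproducing the plan's figures.**
- Test against 70%: n = [(2.2414·√(0.70·0.30) + 1.2816·√(0.85·0.15)) / 0.15]² = 97.98, so 98. The plan's figure is matched. At one-sided 0.025 the same formula gives 81.7, so 82.
- Comparison with placebo (50% v 75%, odds ratio 3, two-sided 0.025): the log-odds-ratio formula gives 95.98, so 96. Matched.
- Allowance: 98 × 1.10 = 107.8, so 108. Matched.

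**Power formula.** Power = Φ{[(p − 0.70) − z·√(0.21/n)] / √(p(1 − p)/n)}. Under the non-responder rule with a share d imputed, p = 0.85 × (1 − d) and n = 108. This assumes that missingness is independent of response.

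Worked case, d = 10%: p = 0.765; √(0.21/108) = 0.0441; √(0.765·0.235/108) = 0.0408. As sized: (0.065 − 2.2414·0.0441)/0.0408 = −0.83, power 20%. As tested: (0.065 − 1.9600·0.0441)/0.0408 = −0.53, power 30%. Exact binomial calculation gives 19% and 34%.

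| Reading | n analysed | Rate analysed | Power, one-sided 0.0125 (as sized) | Power, one-sided 0.025 (as tested) |
|---|---|---|---|---|
| Excluded (SAP 6.8.3), 10% lost | 97 | 85% | 89.6% | 94.8% |
| Non-responder, 2% imputed | 108 | 83.3% | 83% | 90% |
| Non-responder, 5% imputed | 108 | 80.75% | 59% | 71% |
| Non-responder, 10% imputed (worst case) | 108 | 76.5% | 20% | 30% |
| 85% already counts missing as failure | 108 | 85% | 93% | 97% |

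**Where the boundary lies.** With 85% among evaluable subjects, the largest imputed share that keeps 90% at 108 per arm is about 0.7% as sized and 2.1% as tested. If half of the 10% are undosed and leave the FAS, power is 54%/66%.

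**Study level.** These are per-dose figures, and one dose is enough for success. Simulation with both doses at a true 85% and placebo at 50% gives the chance that at least one dose passes both tests (test against 70% as sized / as tested). It is above 99% with 98 evaluable per arm, 82%/94% with 5% imputed at 108, and about 34%/57% with 10% imputed.

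**Comparison with placebo.** With 10% imputed in both arms, 50% v 75% becomes 45% v 67.5%, and power at 108 is about 86–87%. The exposure is almost entirely in the test against 70%.

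**The case against.** A reader might infer that the trial has only 20–30% power. The documents do not support that.
- It would need the whole 10% to be dosed, undeterminable and missing independently of response. Protocol 10.5 does not split drop-out from non-evaluable data, and undosed subjects are outside the FAS.
- The samples that define response are taken from 30 minutes to 4 hours on the dosing day, and the SAP algorithm tolerates one missing intermediate value.
- A subject with an observed PRU of 100 or more in that window is a non-responder whatever else is missing, so imputation costs nothing there.
- The imputed share could therefore be well below 10%. At 2%, power at the planned test level is 90%.

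Two further defences have force. Protocol 10.3.2 and SAP 6.8.1.2 attach the 85% to enrolled or randomized subjects; on that reading missing responses are already absorbed, and power at 108 is 93%/97%. Also, the protocol lets the SAP depart from it, and under SAP 6.8.3 the design works as sized.

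Neither settles the matter. An 85% that already absorbed missing responses would need no 10% allowance, and 10.5 speaks of evaluable subjects, so the documents support both readings. The SAP departure is not declared in section 11, and the SAP's own algorithm points the other way for some subjects.

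A reader might also say that 108 should be 109, because 98/0.9 = 108.9. With a loss described only as about 10%, that is one subject per arm and about 0.4 points of power. It is not a defect worth raising.

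**Conclusion.** The concern stands as a conflict over the primary missing-response rule, with the stated 90% power depending on how it is resolved. The arithmetic behind 96, 98 and 108 is sound. Under exclusion, 108 per arm is adequate (89.6% as sized, 94.8% as tested). Under the protocol's non-responder rule with 85% among evaluable subjects, power falls to 83%/90% at 2% imputed and 59%/71% at 5%, with 20%/30% as the worst case. If the 85% already counts missing as failure, it is 93%/97%.

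The non-responder figures rest on independence of missingness and response, on the imputed subjects being in the FAS, and on the normal approximation. The documents do not give the expected share of dosed subjects with an undeterminable response, so the range from 2% to 10% is an assumption.

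**What to change.** 1. State one missing-response rule for the main analysis, in the same terms, in protocol 10.3.1 and 10.3.2.2 and SAP 6.8.1.1 and 6.8.3. If the rule is exclusion, the SAP algorithm needs a not-determinable outcome in place of NO for those subjects.
2. List any departure from the protocol, with its justification, in SAP section 11.
3. Say whether the 85% refers to evaluable subjects or to all dosed subjects.
4. Restate the power for the test against 70% in protocol 10.5 and the synopsis under that rule, at the alpha actually used for the test (one-sided 0.025 as now planned). If non-responder counting is kept with an evaluable-subject 85%, show power over a range of imputed shares.

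The cost is wording and possibly a less favourable stated power. No extra patients are needed.
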